### **3. METHODOLOGY, ETHICS AND PLANNING**

#### **3.1. METHODOLOGY AND PROCEDURES**

Research design. This project corresponds to an evaluation of the preliminary effectiveness and feasibility of a multi-component pilot intervention. The program will be evaluated through a cluster randomized controlled trial (RCT)

The project activities are organized around two clearly defined stages: one of participatory construction, and another of evaluation of the effectiveness and feasibility of the pilot intervention. They are explained in detail below.

Effectiveness is studied through a mixed design (subtype DEXPLIS, explanatory design sequence), which begins with a quantitative study of quasi-experimental type (comparing equivalent intervention and control facilities) and is followed by a qualitative study to analyze the implementation process and results of the pilot to intervention(including its barriers and facilitators).

The reliability is studied through indicators of participation of teachers in the intervention (initial interest and retention over time), by the satisfaction of teachers and those who participate in the articulation of local health-education networks, and with the analysis of barriers and facilitators at all levels.

Universe and sample. The universe to which the results of this study could be extended are public educational establishments. For this study, two neighborhoods of the commune of Valparaíso were selected. Therefore, the selection of the territories is not random, but the selection of the 2 establishments in each territory is. The inclusion criteria are that they are public schools and have 1st to 8th levels of primary education. The list of establishments that exist in that sector and that meet the inclusion criteria will be taken and will be selected using some random method, 2 schools of each neighborhood (4 in total) will be initially assigned to the intervention and 2 will serve as a control (four in total). As previously described, in a second moment the intervention will be carried out in the establishments that served as control for ethical reasons.

To calculate the necessary sample size, the following parameters were considered: a prevalence of mental disorders of 27.8% and an identification rate of 30% of these cases (9 cases per 100 children, per year). This indicator (which corresponds to scenario 2 and specific objective 4) was taken as one of the most important achievements and reflects the impact of the intervention as a whole. To accept the fulfillment of our hypothesis, it will be necessary to double the identification rate to 60% of cases (18 cases per 100 children, per year). In this way, it is a comparison of proportions, where:  $p_1 = 0.3$ ,  $p_2 = 0.6$ , a confidence level of 95% for a unilateral test and a power level of 90%, 56 children are needed in each group. However, it is expected to work with a much larger sample: if it is considered that in each establishment there are 30 children per grade and only one course per level (from 1st to 8th grade). This would lead us to a potential sample of 240 children per establishment, which implies 480 in intervention facilities and 480 in control facilities.

Development of fieldwork. The development of the fieldwork has three fundamental stages: 1) Implementation of the ECO-Neighborhood Network strategy in the 1 selected neighborhood, (months 1

to 18), 2) the participatory construction of the components of the intervention (months 12 months); and 3) pilot-level evaluation of this intervention (months 12-24).

1. The first stage (months 1 to 18) The component of the intervention aimed at articulating educational establishments with mental health devices (CESFAM teams and secondary level in Health), within specific territories, whose purpose is to expedite the care of these children, will be implemented. It is the so-called ECO-Barrio Network, for whose implementation a working committee will be formed for each sector where the study is implemented, with representatives of all these institutions, in addition to the I. Municipality of Valparaíso. This committee will begin by analyzing the barriers that hinder the referral of children with mental health problems, and then establish a specific work plan in each sector (with objectives, activities, goals and deadlines). The activities of this plan will be implemented in parallel to the intervention with the teachers, in the second part (months 7 to 18, so that the times are concordant). In addition, follow-up meetings of referrals will be held with 1 representative of each CESFAM with ECO BARRIO coordinator and the 4 schools intervened, in a modality that includes virtuous meetings with bimonthly frequency. Finally, this stage of work will include at least one weekly meeting of the FONIS team with advisors and coordinators of RED ECO and Literacy Program.
2. The second stage (months 1 to 12) consists of the participatory construction of the contents of a training program on children's mental health, aimed at teachers of public educational establishments, which will use e-learning (with asynchronous and synchronous activities) and whose contents will be based on their experience with respect to of the problems they distinguish, the way they identify them, the obstacles they have in handling them, and the opportunities for support they can provide (including the relationship with their parents). To collect the experience of the teachers, a working group will be created in each establishment participating in the project, which will collect the experience of the teachers on this subject. In addition, in-depth individual interviews will be conducted. Then, one or two teachers from each group (from each establishment) will be invited to participate in a team with psychologists and psychiatrists from the project, to design the course together. The contents and methods of the course will be made by the research team, under the supervision of the team that includes teachers, technical advisors and audiovisual equipment.
3. The third part (months 12 to 24) consists of carrying out a pilot test taking 4 educational establishments located in two different territories of the commune of Valparaíso, in which the intervention will be carried out, and its results will be compared with 4 other equivalent educational establishments, from those same territories, which serve as control. Pre- and post-intervention assessments will be carried out, using a children's mental health knowledge survey, while referrals from facilities to the corresponding CESFAM will be recorded. Results will be compared between intervention and control results. Information is also collected to assess the participation of teachers in the intervention (feasibility analysis).

At the end of the intervention in the establishments that were the object of it, the quantitative indicators and results that were collected will be synthesized, and a qualitative analysis will be carried out (DEXPLIS design), based on discussion groups that involve the interested parties (teachers, mental health professionals and managers of both sectors). in which the results and achievements will be analyzed, barriers and facilitators of the process will be established, all of which will allow to complete the evaluation in a participatory way and to improve the components of the intervention, based on the empirical experience carried out.

After the end of the intervention, the intervention will also be carried out in its two components (teachers and health-education network) in the 4 establishments that served as control. In this way, an ethical requirement of not depriving the rest of the participants of a beneficial intervention is met. (Months 18 to 24)

Indicators, instruments and analysis procedures. For the detailed description of this point, the effectiveness analysis and the feasibility analysis of the pilot intervention are separated.

1) Evaluation of the effectiveness of the intervention. The effectiveness evaluation is based on comparing the following indicators between intervention and control establishments.

- a) Level of knowledge of the teachers, using an *ad hoc* questionnaire, which is built in the phase prior to the intervention and validated by this team (which incorporates teachers). The conceptual framework of literacy in child and adolescent mental health will be used. This questionnaire will include all the aspects that are part of the training program aimed at teachers and will allow them to obtain scores for their different modules or dimensions. A test and semantic adaptation will be carried out with teachers from establishments in other sectors of the commune, which do not participate in the project, prior to its use within the project. It is expected that in the initial assessment (baseline), the results will be similar in the teachers of the intervention and control establishments. At the end of the intervention it is expected that scores have improved significantly in intervention facilities and have not changed in control facilities.
- b) Rates of referral of mental health problems in children. In each project establishment (intervention and control) a centralized register will be kept of the children indicated by their teachers who require mental health care during the intervention. This will also allow for centralized coordination for referral to the relevant CESFAM. In this way the detection rate can be calculated.
- c) Waiting time between referral from the educational establishment to professional care at the corresponding CESFAM. This indicator is obtained from the centralized register in each educational establishment, which includes the date on which it coordinated with CESFAM for its attention, and the registration of the first attention in the latter. The time elapsed between the two is the waiting time that will be used as an indicator.
- d) Rate of accuracy for referral of children with suspected psychiatric disorders from the school to health care. Each “case” referral will apply the Strength and Difficulties Questionnaire (SDQ). 25 items (scale 0-2).

2) Evaluation of the feasibility of the intervention. Feasibility assessment uses a combination of quantitative (indicator) and qualitative methods, which are described below.

- a) Level of interest of teachers in the intervention: It is estimated through the percentage of teachers who agree to start the training course, out of the total number of teachers who were invited (which would be the totality of each educational establishment).

$$(1) \frac{\text{Teachers who accept}}{\text{Total Teachers}}$$

- b) Level of retention of teachers in the intervention. It is estimated through the proportion of teachers who complete the course of all those who started it. The retention rate for each phase will be described.

- i)  $\frac{\text{Teachers who completes the course}}{\text{Teachers who initiate the course}} \Rightarrow$  description for each phase

- c) Level of satisfaction of teachers with the intervention. An ad hoc survey will be used, with Likert questions for each module or component of the training course, and differentiated for each phase if necessary. The survey will also include open questions, which allow the opinions of the participants to be collected, all with a view to improving them in subsequent versions.
  - i)
- d) Level of satisfaction of the different participants in the intervention of articulation of the health-education network. It will proceed in a similar way to the previous one, using an ad hoc survey (with Likert type questions) and open questions, to collect opinions that seek subsequent improvements.
- e) Barrier analysis and facilitators. This analysis is qualitative and is obtained as part of the DESPLIX design. It is obtained from discussion groups involving all stakeholders (teachers, health and mental health professionals, and health and education managers), in which the results and achievements will be analyzed (based on information from all previous indicators, effectiveness and feasibility), identifying barriers and facilitators of the process.

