### 3.3. WORK PLAN

Specific Objective	Activity	Months																							
		1	2	3	4	5	6	7	8	9	10	11	12	13	14	15	16	17	18	19	20	21	22	23	24
1-Build in a participatory way the contents of a Literacy program in CMH	1-Presentation of the Ethics Committee Project	x																							
	2- Random selection of the 4 PS		x																						
	3-Contact and invitation to working meetings of key informants of the territories and PS		x	x																					
	4- Establish work teams in each selected PS			x																					
	6- Participatory design of the literacy program			x	x	x	x																		
2. Implement the ECO-Barrio network strategy	1- Contact with key agents of the CMH network	x																							
	2-Form a committee in each sector with the representatives of the institutions of the intersectoral ecosystem in CMH	x																							
	3- Develop a participatory work plan with objectives, goals, activities, deadlines and managers.		x	x	x																				
	4-Bimonthly work and follow-up meetings.			x	x	x	x	x	x	x	x	x	x	x	x	x	x	x	x						
3. Assess whether the literacy program significantly improves knowledge in CMH	1- Recruitment of teachers to participate in the literacy intervention.			x	x	x	x																		
	2- Development of knowledge instrument in CMH			x																					
	3-Test of application of the instrument in PS of non-intervened sectors.				x																				
	4-Semantic adaptation of the instrument.					x																			
	5-Implementation of online literacy course (G1 and G2)							x	x	x	x	x	x	x	x	x	x	x	x						
	6 Evaluation of teachers intervened with instrument (pre and post intervention)							x					x							x					
4- Evaluate if the detection rate of CMH problems is significantly improved	1-Random selection of 2 PS similar to those selected in a neighborhood where the intervention has not been implemented				x																				
	2- Determine the detection rate in schools that received the literacy program compared to control schools												x										x		
5.Evaluate whether the relevance of referral to	1- Determine how many of the referred children enter Mental Health treatment (regardless of the device or level of complexity)						x	x	x	x	x	x	x	x	x	x	x	x	x						

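### Schools are allocated 2 v 2 within each neighbourhood, but the comparison described carries neither school nor neighbourhood; reconcile the allocation, then state a school-level analysis with a neighbourhood term

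*Combined protocol and SAP*

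**What the plan says.** Section 3.1 (Universe and sample) describes the allocation: "2 schools of each neighborhood (4 in total) will be initially assigned to the intervention and 2 will serve as a control", four control schools overall. The third fieldwork part in the same section agrees: for the four intervention schools, "its results will be compared with 4 other equivalent educational establishments, from those same territories, which serve as control". The study is called cluster randomised.

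The analysis text is short. "The effectiveness evaluation is based on comparing the following indicators between intervention and control establishments", and, for the pilot test, "Results will be compared between intervention and control results". The indicators are teacher knowledge, referral (detection) rate, waiting time and referral accuracy. The only statistical specification is in the sample-size paragraph: "In this way, it is a comparison of proportions", 0.30 against 0.60, with 56 children per group. No stratum, block, covariate or cluster term is mentioned anywhere.

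Other places do not fit the 2 v 2 structure:

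- Section 2.1 speaks of 8 schools in each neighbourhood.
- The sample-size paragraph counts 480 children per arm at 240 per school, which is two schools per arm.
- The work plan (3.3, objective 4) lists "Random selection of 2 PS similar to those selected in a neighborhood where the intervention has not been implemented".
- Section 2.1 and the fieldwork paragraph of 3.1 place the network in one neighbourhood. The Summary, objective 2 in 2.4.2 and section 4.1.2 place it in two.

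**The concern.** If two schools of each arm sit in each neighbourhood, a difference between neighbourhoods is balanced across the arms and does not bias the estimate. An analysis of school values without a neighbourhood term still leaves that difference in the error. With eight schools, the error term largely decides what can be detected.

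There are reasons to expect a difference. Waiting time is measured to "professional care at the corresponding CESFAM", and 3.1 gives each sector its own committee and work plan. At stake is whether the trial uses the precision that its allocation offers, and whether the analysis is fixed before results can influence it.

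**Working it through.** **1. The plan's own figure.** Inputs from 3.1: p1 = 0.30, p2 = 0.60, 5% level, 90% power, mean p = 0.45.

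n = [z_a·√(2·0.45·0.55) + z_b·√(0.3·0.7 + 0.6·0.4)]² / 0.30²

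- Two-sided: (1.960·0.7036 + 1.2816·0.6708)² / 0.09 = 55.7, so 56. This matches the plan.
- One-sided, as the text words it: (1.645·0.7036 + 1.2816·0.6708)² / 0.09 = 45.2, so 46.

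The stated 56 is therefore the two-sided figure. It is a child-level calculation with no school or neighbourhood in it.

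**2. Neighbourhood in that child-level test.** A difference d between neighbourhoods inflates the null variance by 0.2475 / (0.2475 − d²/4). That is 1.0025, 1.010 and 1.042 for d = 5, 10 and 20 points. One-sided power at 56 per group and d = 10 points is 0.9485 without stratifying and 0.9494 with it. At 480 v 480, 9% v 18%, d = 10 points, it is 0.9935 v 0.9938. The loss is negligible.

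**3. School in that child-level test.** Design effect = 1 + (240 − 1)·ICC. The ICC is not in the documents; 0.01 to 0.10 is assumed. The true one-sided error of a nominal 5% test is 1 − Φ(1.645/√DE).

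| Assumed ICC | Design effect | True one-sided error |
|---|---|---|
| 0.01 | 3.39 | 0.19 |
| 0.05 | 12.95 | 0.32 |
| 0.10 | 24.9 | 0.37 |

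So that test is anti-conservative, because it ignores school.

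**4. School-level analysis, 4 v 4.** Let w be the between-school variance within a neighbourhood and D the neighbourhood difference in units of √w. The arm difference has variance w(1/4 + 1/4) = w/2 with or without the term, and the estimate is the same. Omitting the term adds a sum of squares of 8·(D/2)² = 2D² (in units of w) to the residual. Over 6 df, the residual variance becomes w(1 + D²/3). Including it leaves 8 − 3 = 5 df. The ratio of 95% CI widths, with the term to without it, is (2.571/2.447)/√(1 + D²/3).

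Power and error by simulation, one-sided 5%, assumed effect 2√w:

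| D (SD) | Power without term | Power with term | Type I error without term | CI ratio |
|---|---|---|---|---|
| 0 | 80% | 78% | 5.0% | 1.05 |
| 1 | 72% | 78% | 3.2% | 0.91 |
| 1.5 | 61% | 78% | 1.8% | 0.79 |
| 2 | 48% | 78% | just under 1% | 0.69 |

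Power breaks even at about 0.5 SD. CI width breaks even where 1 + D²/3 = (2.571/2.447)², that is D ≈ 0.56.

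**5. The same on the plan's rates,** 9% v 18%, 240 children per school. School SD = √{0.135·0.865·DE/240}, which is 0.041 at ICC 0.01 and 0.079 at ICC 0.05. Power without v with the term:

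| Assumed ICC | D = 0 | D = 0.5 SD | D = 1 SD | D = 2 SD |
|---|---|---|---|---|
| 0.01 | 0.87 v 0.85 | 0.85 v 0.85 | 0.80 v 0.85 | 0.59 v 0.85 |
| 0.05 | 0.41 v 0.40 | 0.39 v 0.40 | 0.32 v 0.40 | 0.15 v 0.40 |

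**6. If the allocation is not 2 v 2.** With two schools per arm (480/240 = 2), one of each arm per neighbourhood, there are four values. The term then leaves 1 df instead of 2, and the one-sided critical t rises from 2.92 to 6.31. If the control schools come from another neighbourhood, as the work plan has it, arm and neighbourhood coincide and the term cannot be fitted.

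**The case against.** The strongest reply is that the plan specifies no unadjusted analysis. It names no model at all, and a comparison between intervention and control establishments does not exclude one made within neighbourhoods. That stands: the defect is an unspecified analysis.

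A reader might infer that power is certainly lost. The documents do not support this, because they give no neighbourhood difference and no between-school SD. Below about 0.5 SD the term gains nothing or costs slightly.

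A reader might also infer that the planned test is too conservative. That is true only of a school-level test without the term. The one test described is at child level, and ignoring school makes it anti-conservative.

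Nor does the point cover every objective: objective 5 (2.4.2) is an 80% threshold, although referral accuracy is also listed among the indicators compared between arms.

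The 2 v 2 premise is itself contradicted elsewhere, which also stands. So does the caution on waiting time. If the network runs in one neighbourhood only, neighbourhood is the network exposure, and the term would absorb its effect. If it runs in both, schools of both arms may refer to the same CESFAM, and no neighbourhood term cures that.

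That this is a pilot lowers the stakes. It does not remove the case for writing the analysis down beforehand.

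**Conclusion.** The concern holds in a conditional form. Section 3.1 describes allocation within neighbourhoods, and the comparison it describes carries neither school nor neighbourhood. If the 2 v 2 design is confirmed and the analysis is on school values, the term protects against a loss of about 6 points of power at a neighbourhood difference of 1 between-school SD and about 30 points at 2 SD. The price is about 2 points of power and a 5% wider interval if the neighbourhoods are alike. These figures rest on an assumed effect of 2 between-school SDs. With the plan's own rates and assumed ICCs of 0.01 and 0.05, the gain is 5 to 8 points at 1 SD and 25 to 26 points at 2 SD. There is no bias either way. The omission of neighbourhood and the arithmetic are firm; the size of the gain in this trial is unknown.

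**What to change.** First reconcile two facts across the document: how many control schools there are and where they are (2.1, the sample-size paragraph and 3.3 against the allocation and pilot-test text of 3.1), and whether the network runs in one neighbourhood or two.

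Then, if two schools per arm in each neighbourhood is confirmed:

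- State that allocation is stratified by neighbourhood.
- State that each between-arm effectiveness indicator is analysed on the eight school-level values with arm and neighbourhood terms, on 5 residual df. This also makes the school the unit of analysis.
- The average of the two within-neighbourhood differences gives the same estimate and is an acceptable alternative. If its error is pooled within the four arm-by-neighbourhood cells, it has 8 − 4 = 4 df, so name which error is used.
- For waiting time, use the neighbourhood term as a nuisance adjustment only if the network operates in both neighbourhoods, and acknowledge that both arms may share a CESFAM.

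The cost is the reconciliation, a few sentences of analysis text, and 1 of 6 degrees of freedom. If the design proves to be two schools per arm, or to have controls in another neighbourhood, this model should not be adopted as written.

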## **2.3. RESEARCH HYPOTHESES OR ASSUMPTIONS**

1. Teachers who participate in a Child Mental Health Literacy program are able to significantly improve their knowledge regarding the identification of these problems and the delivery of first aids.
2. The establishments that participate in this training program significantly improve the detection rate of children with mental health problems.
3. The relevance of the diagnosis made by teachers when referring children with mental health problems to the corresponding CESFAM is greater than 80%.
4. The health-education networks where an intervention is carried out to articulate the referral of girls and girls with mental health problems, reduce the waiting time that goes between the referral and the first health care.

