### **2.4.2. SPECIFIC OBJECTIVES**

1. Build in a participatory way the contents of a literacy program in Child Mental Health (CMH) with teachers of Public Educational Establishments (PS) and key actors, from the commune of Valparaíso.
2. Implement the strategy of articulation in a network of CMH (ECO-Neighborhood Network) between schools, Primary and Secondary Health Care, Municipality, collaborating agencies of SENAME and other relevant programs in 2 territories of the commune of Valparaíso.
3. To evaluate whether the Child Mental Health Literacy program, aimed at teachers in public educational establishments, manages to significantly improve their knowledge in this regard.
4. To assess whether teachers participating in the CMH Literacy program significantly improve the detection rate of these problems among their pupils.
5. To evaluate whether the relevance of the research for referral from educational establishments to the corresponding CESFAM is greater than 80%.
6. To evaluate whether the health-education articulation strategy (ECO-Barrio Network) significantly improves waiting times between referral and the first care received by a child with a possible mental health problem.
7. Evaluate indicators of feasibility of the multicomponent intervention, which are useful for a future escalation (interest of teachers to participate, retention in the intervention, degree of satisfaction of all participants, facilitators and perceived barriers).

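### No single contrast decides effectiveness: detection sizes the study but is not named primary, its date is not fixed, and the later marked date falls while control schools are receiving the intervention

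*Combined protocol and SAP*

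**What the plan says.** Section 2.4.1 sets one general objective: to evaluate the effectiveness and feasibility of the multicomponent intervention. Section 3.1 (indicators, instruments and analysis procedures) states how effectiveness is judged: "The effectiveness evaluation is based on comparing the following indicators between intervention and control establishments". Four indicators follow, without ranking: teacher knowledge, referral (detection) rate, waiting time and accuracy of referral.

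Significance is asked of three of them.

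- **Knowledge:** hypothesis 1 says that trained teachers "are able to significantly improve their knowledge regarding the identification of these problems and the delivery of first aids"; objective 3 repeats the claim.
- **Detection:** hypothesis 2 reads "The establishments that participate in this training program significantly improve the detection rate of children with mental health problems"; objective 4 repeats it.
- **Waiting time:** objective 6 asks whether the network strategy "significantly improves waiting times between referral and the first care received by a child with a possible mental health problem". Hypothesis 4 speaks of a reduction but not of significance.

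Hypothesis 3 and objective 5 set a different kind of criterion for referral relevance, a threshold of more than 80%.

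The sample-size paragraph in section 3.1 uses detection, with "an identification rate of 30% of these cases" to be doubled to 60%, and says that this indicator "was taken as one of the most important achievements and reflects the impact of the intervention as a whole". It is the only place where an error level appears: "a confidence level of 95% for a unilateral test and a power level of 90%, 56 children are needed in each group".

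The work plan (section 3.3, objective 4) lists the activity "Determine the detection rate in schools that received the literacy program compared to control schools" with two marks, at months 12 and 22 by column count. Section 3.1 places delivery of both components to the control schools in months 18 to 24.

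**The concern.** Nothing in the plan says which indicator, at which date, settles whether the programme is effective. No indicator is called primary, secondary or exploratory, no testing order is given, and the stated 5% is not divided.

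The indicators can easily disagree. The knowledge questionnaire is built to cover every aspect of the course, so it is the measure most likely to move. Detection and waiting time depend on what happens in schools and health centres afterwards. Without a named contrast, a gain in knowledge only, or a chance gain on one indicator or date, could be reported as effectiveness of the whole programme. The Summary says that the results will be used to design a larger study, and section 3.2.1 mentions possible national scale-up.

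The two detection dates add a second difficulty. They do not answer the same question, because at the later one the control schools are themselves in the intervention period.

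**Working it through.** **1. The plan's own figure.** Inputs from section 3.1: p1 = 0.30, p2 = 0.60, 90% power. With pooled variance under the null,

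n = [z_α √(2·p̄·q̄) + z_β √(p1q1 + p2q2)]² / (p2 − p1)², with p̄ = 0.45.

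Here √(2 × 0.45 × 0.55) = 0.7036, √(0.21 + 0.24) = 0.6708 and z_β = 1.2816.

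- One-sided 5% (z = 1.645): (1.157 + 0.860)² / 0.09 = 45.2, so 46 per group (52 with continuity correction).
- Two-sided 5% (z = 1.960): (1.379 + 0.860)² / 0.09 = 55.7, so 56 per group.

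The stated 56 is therefore reproduced by a two-sided test, although the text says unilateral. That is a separate matter, but it bears on the sensitivity check in step 4.

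**2. Three significance claims, each at one-sided 5%.** The level is stated for detection only; using it for knowledge and waiting time is an assumption. All nulls are taken as true, with a common correlation ρ between test statistics. The documents give no ρ, so a range is shown.

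Chance of at least one false positive = 1 − E[Φ((c − √ρ·Z)/√(1 − ρ))^k], with c = 1.645 and k = 3. At ρ = 0 this is 1 − 0.95³ = 0.143.

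| ρ | k = 3 |
|---|---|
| 0 | 14.3% |
| 0.5 | 11.8% |
| 0.8 | 9.3% |

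**3. Detection alone, at both dates (k = 2).** At ρ = 0, 1 − 0.95² = 9.8%; at ρ = 0.5, 8.8%; at ρ = 0.9, 6.8%.

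**4. Sensitivity to sidedness.** If the tests are really two-sided 5%, each has 2.5% in the favourable direction. Three tests then give a false favourable finding with probability 1 − 0.975³ = 7.3% at ρ = 0, 6.3% at ρ = 0.5 and 4.9% at ρ = 0.8.

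**5. The dates side by side.** Section 3.1 puts the pilot evaluation in months 12 to 24 and control-school delivery in months 18 to 24. The work plan runs the online course (two groups, G1 and G2) over months 7 to 18 and marks detection at months 12 and 22. Month 22 is inside the control schools' intervention period. Month 12 is the start of the pilot evaluation in section 3.1, but mid-way through the course period in the work plan. The two sections do not agree on a timetable from which one clean comparison date can be read.

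**The case against.** The strongest defence is that objectives 3, 4 and 6 are separate questions: the course and knowledge, trained teachers and detection, the network and waiting time. Testing each at its own level is defensible if each is reported on its own. Detection is also close to primary already: it drives the sample size, has an acceptance rule, and is said to reflect the intervention as a whole. And the study is a pilot of preliminary effectiveness, where strict family-wise control is not usually required.

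Much of this stands and limits the severity. It does not remove the gap, because section 3.1 pools the indicators into one effectiveness evaluation, never calls detection primary, and leaves its date open.

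A reader might infer more than the documents support:

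- *That three hypotheses each claim significance at full alpha.* Only hypotheses 1 and 2 use that language; for waiting time it is in objective 6. The 5% level is given for detection alone.
- *That the plan will declare success on any one result.* No passage says so; the plan merely does not exclude it.
- *That the error rate is 12% to 19%.* The upper part counts a fourth test (18.5% at ρ = 0, 14.4% at ρ = 0.5). The second detection date is a weak candidate for that: it is read from column positions, the activity is to determine a rate rather than to test it, and the date is contaminated. The range also leaves out higher correlations.
- *That eight schools make a split alpha unattainable, or that requiring every test to succeed costs a known amount of power.* The first assumes a randomisation test, and the second assumes powers for knowledge and waiting time. The plan states neither.

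**Conclusion.** The point holds as a failure to name the deciding contrast and its date. If the three significance claims are each tested at one-sided 5% and any one may support effectiveness, the chance of at least one false positive is about 9% to 14% instead of 5%. If only detection is used but either date may count, it is about 7% to 10%. These figures rest on an assumed level for knowledge and waiting time, an any-one-suffices rule that the plan leaves open but does not state, and correlations that the documents do not supply. With two-sided tests the excess of favourable false findings over 5% is smaller, and at ρ = 0.8 it vanishes.

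The problem with the later date needs no probability assumption, only the column reading of the work plan: a comparison at month 22 is made while control schools are scheduled to receive the intervention. Severity is minor to moderate, given the pilot status.

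**What to change.** In the sample-size paragraph and the effectiveness-evaluation paragraph of section 3.1, state that the between-arm difference in detection rate, at one named date before control schools receive the intervention, is the single primary contrast, tested at the stated one-sided 5%. Report the later detection date descriptively. Before naming the date, reconcile the work plan in section 3.3 with the timing of the pilot and of control-school delivery in section 3.1.

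Label knowledge, waiting time and referral accuracy (with its criterion of more than 80%) as secondary or exploratory, reported as estimates with 95% confidence intervals, and align hypotheses 1, 3 and 4 and objectives 3, 5 and 6 with that status. If confirmatory claims on knowledge and waiting time are wanted, test them in a fixed order after detection, stopping at the first non-significant result.

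This needs wording only, with no extra schools, children or data, and should be settled before results are seen. The cost is that a gain in knowledge or waiting time without a gain in detection could be reported only as supportive.
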